8.3 PRESENTATION

The efficacy summary will include the following:

- Number and percentage of subjects who died before the first response assessment
- Number and percentage of subjects who had at least one response assessment per RECIST 1.1
- Number and percentage of each response (i.e. CR, PR, SD, PD, NE) as the best overall response per RECIST 1.1
- Observed objective response rate (per RECIST 1.1) and the 95% Clopper-Pearson confidence interval
- Number and percentage of subjects who had at least one response assessment per iRECIST
- Number and percentage of each response (i.e. iCR, iPR, iSD, iUPD, iCPD, NE) as the best overall response per iRECIST
- Observed objective response rate (per iRECIST) and the 95% Clopper-Pearson confidence interval

9 SAFETY ANALYSIS

The safety analysis set will be used for data summaries and listings in this section.

9.1 ADVERSE EVENTS

Adverse events (AEs) will be coded to the system organ class (SOC) and preferred term (PT) using MedDRA version 25.1. Toxicity grading is based on the National Cancer Institute Common Terminology Criteria for Adverse Events (NCI CTCAE) version 5.0.

All AE summaries will be limited to the treatment-emergent adverse events (TEAEs). A TEAE is defined as an AE that has an onset or a worsening in severity during or after the first dose of study drug and up to 30 days after the last dose of study drug, or one day prior to the subsequent anti-tumor therapy, whichever occurs earlier. An AE that has a change in severity will be recorded as two separate AEs on the CRF under the same SOC/PT of different severity levels. If an AE has a missing onset date, it will be considered as a TEAE in the below situations:

- An AE whose onset date and end date are both missing.
- An AE where the onset date is missing and the end date is after the first dose date of study drug
- An AE where the onset date is missing, the end date is on the first dose date of study drug, and the end time (hh:mm) is absent or after the initiation of the first dose of study drug.

An overall summary of TEAEs will be presented to include the number and percentage of subjects with at least 1 TEAE in the following categories:

- Any TEAE
- Serious TEAE
- TEAE of CTCAE grade ≥ 3
- TEAE of maximum CTCAE Grade 3
- TEAE of maximum CTCAE Grade 4
- TEAE of maximum CTCAE Grade 5
- Infusion-related reaction
- TEAE related to any study drug
- TEAE related to TJ004309
- TEAE related to atezolizumab
- Serious TEAE related to any study drug
- Serious TEAE related to TJ004309

- Serious TEAE related to atezolizumab
- TEAE of CTCAE grade ≥ 3 related to any study drug
- TEAE of CTCAE grade ≥ 3 related to TJ004309
- TEAE of CTCAE grade ≥ 3 related to atezolizumab
- TEAE leading to any study drug discontinuation
- TEAE leading to TJ004309 discontinuation
- TEAE leading to atezolizumab discontinuation
- TEAE leading to death

In addition, the number and percentage of subjects with at least one TEAE in the following categories will be summarized by SOC and PT (unless noted otherwise below) for each cohort and overall:

- Any TEAE (summarized by SOC, PT and maximum CTCAE grade)
- Serious TEAE
- TEAE of CTCAE grade ≥ 3 (summarized by SOC, PT and maximum CTCAE grade)
- TEAE of CTCAE grade ≥ 3 related to any study drug (summarized by SOC, PT and maximum CTCAE grade)
- TEAE of CTCAE grade ≥ 3 related to TJ004309 (summarized by SOC, PT and maximum CTCAE grade)
- Infusion-related reactions
- TEAE related to any study drug
- TEAE related to TJ004309
- TEAE related to atezolizumab
- Serious TEAE related to any study drug
- Serious TEAE related to TJ004309
- Serious TEAE related to atezolizumab
- TEAE leading to any study drug discontinuation
- TEAE leading to TJ004309 discontinuation
- TEAE leading to atezolizumab discontinuation
- TEAE leading to death

SOC/PT categories in the TEAE summaries will be sorted in a frequency decreasing order for overall. A subject who had multiple TEAEs in a SOC/PT category will only be counted

once for that category. The causal relationship between the treatment and an AE will be assessed by the Investigator. For summary purposes, if relationship to the treatment is missing for a TEAE, it will be assumed to be related to the treatment; if the CTCAE grade is missing for a TEAE, it will be assumed to be grade 3; if a subject experienced multiple TEAEs in the same SOC/PT category, the maximum CTCAE grade and the strongest causal relationship to treatment among these TEAEs will be used.

All AEs collected on the CRF page 'Adverse Events' will be listed by subject.

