**Duration of Subject Participation in the Study:**

Planned screening duration: approximately 4 weeks.

Planned treatment duration: patients are eligible for treatment until clinically significant disease progression, unacceptable toxicity, or subject/Investigator decision to withdraw.

Planned follow-up safety evaluation: at least 30 days following the last dose of study drug(s).

Response/Survival follow-up duration: approximately 2 years from the first dose of study drug.

Total duration of study participation: approximately 120 weeks (including response/survival follow-up).

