- g) For Cohort 2 only: Pre-treatment and paired on-treatment fresh tumor biopsies will be collected from at least 5 patients. CD73 enzymatic activity and assessment of proteins in the adenosine pathway (e.g., CD73, A2A receptor, and whole genome gene expression profiles) will be assessed in fresh tumor biopsies. Biopsy must be excisional, incisional, or core. Fine needle aspiration is insufficient. Samples will be collected prior to dosing and processed and shipped within 24 hours according to separate laboratory manual. The tumor biopsy samples must complete testing for the following infectious diseases within 28 days of tumor biopsy collection: Hepatitis B, Hepatitis C, Tuberculosis, HIV, Syphilis, and COVID-19 and confirmed to be negative. Testing is to be performed locally.
- h) Initially, TJ004309 will be administered over 1 hour ( $\pm$ 15 minutes) in Cycles 1 and 2. In the absence of IRRs in patients infused over 1 hour in Cycle 2, the infusion time of TJ004309 may be reduced to 30 minutes ( $\pm$ 10 minutes) per Investigator's discretion. Infusion timing should be close to the instructed infusion time as possible.
- i) Adverse events should be documented and recorded at each visit using the NCI CTCAE Version 5.0.
- j) All medications used by the patient including prescription drugs, over-the-counter drugs, and herbal/homeopathic remedies and therapies taken from 28 days prior to the first study drug dose are to be documented as prior medications.
- k) A full physical examination will be performed at Screening and at pre-dose of Cycle 1 Day 1, unless the screening physical examination was performed within the last 7 days.
- l) Abbreviated physical examinations should be performed for all other visits. If indicated, a full physical exam may be performed instead at the Investigator's discretion.
- m) Height will only be recorded at Screening. Doses will be calculated based on the actual weight of each subject, as measured at the Screening Visit. The weight used may be revised to a weight collected at a later date if it has changed by more than 10%.

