### 4.5 Safety Follow-up Period

After the treatment periods, all subjects will enter a safety follow-up period and will be evaluated for safety, tolerability, and tumor response (if applicable) for at least 90 days after the last dose of study drug, or 30 days following cessation of study treatment if the subject initiates new anticancer therapy, whichever is earlier. Subjects will be required to return to the study sites for three (3) safety follow-up visits (approximately 30, 60 and 90 days after the last dose of study drug), except those subjects who withdraw consent for study participation. After treatment discontinuation, in the event of continuing serious adverse events (SAEs), subjects will be followed until resolution or stabilization of the SAEs (regardless of the relationship to the IMP). Any subject who has an ongoing non-serious AE that is possibly related or related to the IMP or study procedures at the 90-day post-treatment Follow-up visit will be followed up, where possible, until resolution or until the unresolved non-serious AE is judged by the Investigator (or designee) to have stabilized. Any subject who has an ongoing non-serious AE that is not related or unlikely related to the IMP or study procedures at the Follow-up visit, can be closed out as ongoing at the Investigator's discretion. If a subject initiates a new anticancer therapy within 30 days after the last dose of study treatment, one (1) Post-Treatment Safety Follow-Up visit should occur approximately 30 days after the last dose of study drug and therefore subsequent follow-up visits will not be required.

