## 6.8 Concomitant Therapy

All prescription and non-prescription medications and therapies, including pharmacologic doses of vitamins, herbal medicines, or other non-traditional medicines, taken from 28 days prior to the first study drug dose are to be documented as *prior* medications. Medications taken from the time of the first study drug dose on C1D1 through 30 days after the last study drug dose are to be recorded as *concomitant* medications in the electronic case report form (eCRF). All therapies for primary diagnosis should be recorded regardless of when they were taken.

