### 8.4.1 Adverse Event Reporting Time Period

All AEs, whether reported by the subject voluntarily or upon questioning, or noted on physical examination, will be recorded from the time the ICF is signed until study completion, 30 days after the last dose of study drug or 30 days following cessation of study treatment if the subject initiates new anti-cancer therapy, whichever is earlier. The event name, date of onset, duration, and severity will be documented, together with an Investigator's (or designee's) opinion of the relationship to study drug.

**Before initiation of study drug**, only the AEs which regarded as have relationship to study procedure will be collected as AE.

All SAEs (regardless of relationship to study drug) and/or non-serious AE considered to be possibly, probably or definitely related to study drug recorded during the course of the study will be followed up, where possible, until resolution or until the unresolved AEs are judged by the Investigator (or designee) to have stabilized. This will be completed at the Investigator's (or designee's) discretion. Medical occurrences that begin before the start of study drug, but after obtaining informed consent, will be recorded on the Medical History/Current Medical Conditions section of the eCRF rather than in the Adverse Event section.

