#### 8.4.6 Follow-up of AE and SAE

Every reasonable effort will be made to follow up with subjects who have AEs. Any subject who has an ongoing SAE (regardless of relationship to study drug) and/or non-serious AE that is possibly, probably or definitely related to the IMP or study procedures at the 30-day post-treatment, follow-up visit or last study visit will be followed up, where possible, until resolution or until the unresolved AE is judged by the Investigator (or designee) to have stabilized. This will be completed at the Investigator's (or designee's) discretion. Any subject who has an ongoing non-serious AE that is not related or unlikely related to the IMP or study procedures at the Follow up visit or last study visit, can be closed out as ongoing at the Investigator's discretion. If a subject initiates new anti-cancer therapy during the follow-up period, new AEs are not required to be reported.

New or updated information will be recorded in the originally completed eCRF.

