3.3 SAFETY FOLLOW-UP PERIOD

After the treatment periods, all subjects will enter a safety follow-up period and will be evaluated for safety, tolerability, and tumor response (if applicable) for at least 90 days after the last dose of study drug, or 30 days following cessation of study treatment if the subject initiates new anticancer therapy, whichever is earlier. Subjects will be required to return to the study sites for three (3) safety follow-up visits (approximately 30, 60 and 90 days after the last dose of study drug), except those subjects who withdraw consent for study participation. After treatment discontinuation, in the event of continuing serious adverse events (SAEs), subjects will be followed until resolution or stabilization of the SAEs (regardless of the relationship to the IMP). Any subject who has an ongoing non-serious AE that is possibly related or related to the IMP or study procedures at the 90-day post-treatment Follow-up visit will be followed up, where possible, until resolution or until the unresolved non-serious AE is judged by the Investigator (or designee) to have stabilized. Any subject who has an ongoing non-serious AE that is not related or unlikely related to the IMP or study procedures at the Follow-up visit, can be closed out as ongoing at the Investigator's discretion. If a subject initiates a new anticancer therapy within 30 days after the last dose of study treatment, one (1) Post-Treatment Safety Follow-Up visit should occur approximately 30 days after the last dose of study drug and therefore subsequent follow-up visits will not be required.

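### The protocol ends AE recording at 30 days in one section and plans it to 90 days in others, and the SAP's imputed therapy date can close the AE table window on the day of last dose

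*SAP*

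**What the plan says.** **Collection period.** Protocol 8.4.1 ends AE recording at the sooner of two points: "30 days after the last dose of study drug or 30 days following cessation of study treatment if the subject initiates new anti-cancer therapy". Protocol 4.5 requires "three (3) safety follow-up visits (approximately 30, 60 and 90 days after the last dose of study drug"), and SAP 3.3 repeats that subjects are "evaluated for safety, tolerability, and tumor response (if applicable) for at least 90 days after the last dose of study drug". Both shorten this to 30 days if new anticancer therapy starts. Protocol Table 2 marks adverse events at the 30-, 60- and 90-day visits, and its footnote i reads "Adverse events should be documented and recorded at each visit using the NCI CTCAE Version 5.0".

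Three other places still use 30 days. The synopsis has "Planned follow-up safety evaluation: at least 30 days following the last dose of study drug(s"), protocol 8.4.6 follows events ongoing "at the 30-day post-treatment, follow-up visit or last study visit will be followed up", and protocol 6.8 records concomitant medication "through 30 days after the last study drug dose". The synopsis figure is a minimum and 8.4.6 also names the last study visit, so these two conflict less sharply with 90 days than 8.4.1 does.

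**Table window.** SAP 9.1 restricts every AE summary to treatment-emergent events, with the window closing "up to 30 days after the last dose of study drug, or one day prior to the subsequent anti-tumor therapy, whichever occurs earlier". Protocol 9.2.5 defines treatment emergence by onset or worsening after dosing and sets no end. SAP 9.1 and 9.2 list all CRF adverse events and all deaths without a window.

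**Missing therapy dates.** SAP 4.5.1 imputes the start of subsequent therapy as last dose + 1 day in three cases: the date is completely missing, only the year is known and it is the same year, or only month and year are known and they are the same. Otherwise it takes the first day of the known month or year.

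**The concern.** Two separate problems meet in the AE tables.

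First, sites cannot follow both protocol 8.4.1 and Table 2. Some may stop recording at day 30 and others may record at days 60 and 90. The SAP uses the 30-day limit without saying which collection period was in force, or that the limit is narrower than protocol 9.2.5. A serious event that starts on day 45 and is collected appears in no table.

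Second, the imputation takes the earliest date after dosing for the next therapy. That can be cautious when a date censors an efficacy endpoint. Here SAP 8 does not report DOR, PFS or OS, and SAP 8.1 and 8.2 end best response at progression or end of treatment. The only stated analysis left that uses the therapy start is the AE window, where an early date removes events from the tables.

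Safety and tolerability is the first secondary objective in both documents, and readers take AE rates and maximum grades from the tables rather than from subject listings.

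**Working it through.** **1. The collection periods side by side**

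| Place | End point after last dose |
|---|---|
| Protocol 8.4.1, AE recording | 30 days |
| Protocol 4.5 and SAP 3.3, safety follow-up | at least 90 days (30 if new therapy starts) |
| Protocol Table 2 and footnote i, AE recording | visits at 30, 60 and 90 days after end of treatment |
| Protocol 9.2.5, treatment emergence | no limit |
| SAP 9.1, all AE tables | 30 days, or the day before subsequent therapy |

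The explicit instruction to record AEs after day 30 is in Table 2 and its footnote; section 4.5 speaks of evaluating safety. For a subject without new therapy, 90 − 30 = 60 days of planned follow-up lie outside the table window. This is a span of time, not a share of events.

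**2. The table window**

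Window end = min(last dose + 30, therapy start − 1).

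With no subsequent therapy this gives day 30, which reproduces the SAP's stated limit. With an imputed start of last dose + 1, it gives (last dose + 1) − 1 = last dose, so 0 post-dose days.

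Example with an assumed last dose of 10 March 2022, so that the 30-day limit is 9 April. The right-hand column uses the latest therapy date consistent with the record and keeps the 30-day cap. Figures in brackets are days after last dose.

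| Therapy start as recorded | SAP date used | Window ends under SAP | Window ends with latest date |
|---|---|---|---|
| No subsequent therapy | none | 9 Apr (30) | 9 Apr (30) |
| 28 March 2022 | 28 Mar | 27 Mar (17) | 27 Mar (17) |
| Completely missing | 11 Mar | 10 Mar (0) | 9 Apr (30) |
| 2022 only | 11 Mar | 10 Mar (0) | 9 Apr (30) |
| March 2022 | 11 Mar | 10 Mar (0) | 30 Mar (20) |
| April 2022 | 1 Apr | 31 Mar (21) | 9 Apr (30) |
| 2023 only | 1 Jan 2023 | 9 Apr (30) | 9 Apr (30) |

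The April row depends on the day of last dose: over last doses from 1 to 31 March, the SAP rule leaves between 30 and 0 days. For a partial date in the month of last dose, the two rules differ by 0 to 29 days.

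**3. What one omitted subject does to a table row**

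If the omitted event is that subject's only one in the row, the row falls by 1/30 = 3.3 points in a full cohort of 30, 1/15 = 6.7 points if Cohort 1 stopped at 15, and 1/60 = 1.7 points over both full cohorts. The denominators are planned sizes, not known enrolment.

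**The case against.** The strongest reply is that the SAP's 30 days are no error. They match protocol 8.4.1, the section that sets the AE reporting period, and the concomitant-medication period in 6.8. This stands: the conflict begins inside the protocol, and the 30-day tables can remain the main tables.

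A reader might infer that the SAP leaves events on days 31 to 90 unhandled. It does not. SAP 9.1 limits tables to treatment-emergent events and lists everything collected, so late events are listed and not tabulated. What is missing is a statement of the collection period followed and of the narrowing against protocol 9.2.5.

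A reader might also infer that a missing therapy date removes all of a subject's AEs, or all post-dose AEs, from the tables. That is too strong. Events up to and including the day of last dose stay. SAP 9.1 also counts an event with missing onset and an end date after first dose, with no upper limit. Only events with known onset after the last-dose day are affected.

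Nor is there a gap over changes in severity. SAP 9.1 says that a change is entered as a second AE record, and protocol 8.4.6 on updating the eCRF does not contradict this.

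Finally, an early therapy date avoids charging the next treatment's toxicity to study drug, and a late date errs the other way. This is a fair trade-off, but the errors are not equal here. Protocol 8.4.6 does not require new AEs to be reported once new therapy starts in follow-up, which limits how many wrong events a later date could add. The current rule discards events before the true therapy start as well as after it.

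**Conclusion.** Both parts hold, as possible under-counting in tables and not as loss of data. Protocol 8.4.1 conflicts with protocol 4.5 and Table 2, and collected events with known onset on days 31 to 90 reach listings only. Followed as written, SAP 4.5.1 and 9.1 together leave a subject whose therapy date is completely missing with 0 post-dose days in the window, against up to 30. The same happens with a partial date in the month or year of last dose.

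The size per subject follows from the rules. The size in the tables does not: the documents give neither the number of subjects with a missing or partial therapy date nor the number of late events, and either may be zero. The calculation reads the imputation rule as comparing last dose + 1 with the partial date; last doses on the final day of a month or year are an edge case and are not used here. ORR is unaffected. Since Part 2 was not started, the report is abbreviated and all events are listed, the point lies between minor and should-fix.

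**What to change.** 1. Reconcile protocol 8.4.1, 8.4.6 and the synopsis with protocol 4.5 and Table 2. State in the SAP which AE collection period the sites followed.
2. Keep the 30-day tables as the main tables, and state that they narrow the definition in protocol 9.2.5. Add one supplementary summary of serious AEs and deaths to 90 days after last dose or the day before subsequent therapy, whichever is earlier. Show deaths from progression separately, because protocol 8.3.2.2 makes progression leading to death reportable as an SAE, and note that collection after day 30 may be uneven.
3. For the treatment-emergent window only, use the latest therapy start consistent with a partial date, and no therapy cut-off when the date is completely missing. Keep the 30-day cap in both cases. Report how many subjects have an imputed date.

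The cost is a protocol clarification, SAP wording, one table and one changed date derivation, with no new data. The downside is that a few events after the true start of new therapy may be counted, within the 30-day cap.

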9.2 DEATHS

Deaths during study and their primary causes will be listed.

9.3 CLINICAL LABORATORY PARAMETERS

Hematology, chemistry, coagulation, thyroid function testing, CA125 test, dipstick urinalysis and microscopic laboratory results will be listed by visit per subject.

9.4 VITAL SIGNS

Vital sign measurements (systolic/diastolic blood pressure, pulse rate, respiratory rate and body temperature) will be listed by visit per subject.

9.5 12-LEAD ELECTROCARDIOGRAM (ECG)

Investigator's overall interpretation of the 12-lead ECG result as normal or abnormal in each assessment will be listed per subject, along with whether the abnormality was clinically significant or not, and the abnormality details if clinically significant.

9.6 ECOG PERFORMANCE STATUS

ECOG performance status will be listed by visit per subject.

9.7 PHYSICAL EXAMINATION

Abnormal physical examination results will be listed per subject.

10 PHARMACOKINETIC/PHARMACODYNAMIC ANALYSES

Pharmacokinetic and pharmacodynamic analyses will not be performed.

11 IMMUNOGENICITY ANALYSIS

Immunogenicity analysis will not be performed.

